***Notes**

1. If patient is in atrial fibrillation or atrial flutter or RA lead is turned off, RA electrical measurements are not required.
2. If patient is pacemaker dependent, RV sensing amplitude is not required.

3. As referenced under the Definitions in section 4.2, abnormal pacing lead impedances are defined as measured pacing impedances with values $\leq 200 \Omega$ or $\geq 2000 \Omega$. RV lead pacing impedances have been observed in typical clinical settings to be in the range of 200-1200 Ω for the majority of patients. However, lead pacing impedances measured up to 1999 Ω are considered to be within the normal bounds of the performance of the RV lead because characteristics such as non-viable myocardium, lead-to-tissue contact, etc., specific to each patient have been known to produce measured pacing impedances that are higher than the observed 1200 Ω noted above.

Device diagnostics and archives of RV lead impedance values may also be used to diagnose potential lead failures. Alternatively, investigators should consult the respective device and lead user manuals, St. Jude Medical technical support or other St. Jude Medical clinical support personnel to diagnose potential lead failures.

In the subset of patients participating in the sub-study, cinefluoroscopy (AP, LAO 45° or the best possible LAO view, RAO 45° or the best possible RAO view) of the entire lead length and the pocket area will be performed at the 24, 36, 48 and 60 month visits. Additionally, query the patient to determine whether the patient has had any chest x-rays or fluoroscopy of the implanted leads since the last visit. Whenever possible, obtain copies of any imaging done (x-ray or fluoroscopy). Review those images for signs of lead conductor externalization. Report those events, as applicable, on an adverse event form. Also, query the patient regarding any adverse events occurring between routine visits. Complete a Follow-up Case Report Form and record all results. Should any adverse event occur, complete an Adverse Event Case Report Form. If any images were obtained (especially for patients participating in the sub-study at the 24, 36, 48 and 60 month visits), complete an Imaging Case Report Form. Submit the forms to St. Jude Medical using the EDC system.

Upload the device session record including all stored IEGMs to St. Jude Medical using the SJM EDC Portal device data upload utility.

10.0 Protocol Deviations

Investigators are required to adhere to the protocol, signed Investigator's Agreement, applicable federal (national) or state/local, laws and regulations, and any conditions required by the IRB/MEC or applicable regulatory authorities.

A protocol deviation is used to describe situations in which the clinical protocol was not followed. All deviations from the protocol must be reported to St. Jude Medical per 21 CFR §812.150. In addition, all deviations must be reported to the reviewing IRB/MEC per the IRB/MEC's reporting requirements.

The investigator must notify St. Jude Medical and the reviewing IRB/MEC of any deviation from the protocol plan to protect the life or physical well-being of a subject in an emergency as soon as possible, but not later than 5 working days after the deviation has occurred, or no later than 5 working days after the investigator becomes aware of the deviation.

Should a deviation occur, complete a Deviation Case Report Form and submit to St. Jude Medical using the EDC system. If a deviation occurs between scheduled visits, the event should be reported at the next scheduled visit. Visits will be considered missed if they are outside of the visit window.

11.0 Adverse Events

Adverse events are any unfavorable clinical event which impacts, or has the potential to impact the health or safety of a patient caused by or associated with a study device or intervention. Adverse events will be classified as complication or observations.

Complications: Adverse events that require invasive intervention (e.g., lead fracture) with the exception of RV lead perforations. All adverse events reported as RV lead perforations (managed with or without an invasive intervention) will be considered a complication. Each complication will be reported in one of the following categories for analysis purposes:

- RV lead related complication: A complication that is related to the RV lead.
- Device related: A complication related to the device
- Other lead related complication: A complication that is related to the LV or RA lead.
- Procedure related complication: A complication related to an implant or system revision procedure.
- Other complication: Any complication that does not fall into one of the categories listed above.

Observations: Adverse events that can be managed without invasive intervention (e.g., oversensing or loss of pacing capture, which is remedied by reprogramming of the pulse generator). Observations will be reported in one of the following categories:

- RV lead observation: An observation that is related to the RV lead.
- Device related: An observation that is related to the device.
- Other lead related observation: An observation that is related to the LV or RA lead.
- Procedure related observation: An observation that is related to an implant or system revision procedure.
- Other observation: Any observation that does not fall into one of the categories listed above.

Should an adverse event occur at any time between implant and withdrawal, complete an Adverse Event form and submit to St. Jude Medical using the EDC system as soon as possible or within 10 days from the date the site became aware of an event. If an adverse event occurs between scheduled visits, the event should be reported at the next scheduled

visit. Report the adverse event to the IRB/MEC per the IRB/MEC policy. Any explanted devices or leads should be returned to St. Jude Medical for analysis.

Possible adverse events (in alphabetical order) associated with leads, devices or implant and/or system revision procedure may include, but are not limited to the following:

- Abnormal lead defibrillation impedance
- Abnormal lead pacing impedance
- Acceleration of arrhythmias (caused by the device)
- Air embolism
- Allergic reaction
- Bleeding
- Cardiac perforation
- Cardiac tamponade
- Chronic nerve damage
- Decompensated heart failure
- Elevated pacing thresholds
- Erosion
- Exacerbation of heart failure
- Excessive fibrotic tissue growth
- Extracardiac stimulation (phrenic nerve, diaphragm, chest wall)
- Failure to detect VT/VF
- Fluid accumulation
- Formation of hematomas or cysts
- Generator malfunction
- Hemothorax
- Inappropriate shocks
- Infection
- Lead/port damage
- Lead fracture
- Lead insulation damage
- Lead migration/dislodgement
- Lead Noise
- Loss of capture
- Failure to deliver therapy
- Loss of sensing
- Myocardial Infarction (MI)
- Oversensing
- Pectoral Stimulation
- Pericardial Effusion
- Pneumothorax
- Thromboemboli
- Undersensing
- Venous occlusion

Patients susceptible to frequent shocks despite antiarrhythmic medical management may develop psychological intolerance to an ICD or CRT-D system that may include the following:

- Dependency
- Depression
- Fear of premature battery depletion
- Fear of shocking while conscious
- Fear that shocking capability may be lost
- Imagined shocking (phantom shock)

For unexpected failure modes or unexpected adverse events, the site should follow their standard reporting practices for medical device reporting (MDR). As defined in 21 CFR 803, a MDR reportable event (or reportable event) means: An event that device user facilities become aware of that reasonably suggests that a device has or may have caused or contributed to a death or serious injury. A device user facility must report deaths and serious injuries that a device has or may have caused or contributed to, establish and maintain adverse event files, and submit summary annual reports to FDA.

12.0 Other Reported Events

Other Reported Events are any other clinical event that is submitted by the investigator which is not caused by or associated with the study device and/or system component(s) and/or defined as an adverse event in section 11.0.

13.0 Health Care Utilization/Hospitalization Visits

All inpatient, urgent care, ER, observational or outpatient visits for cardiac or suspected heart failure reasons which occur after a successful implant of the Optisure RV lead must be reported using the Health Care Utilization Case Report Form.

A Health Care Utilization/Hospitalization Case Report Form must be completed and submitted along with supporting documentation (i.e. Admission/Discharge Summary) to St. Jude Medical using the EDC system.

14.0 Deaths

All patient deaths that occur during this investigation must be reported to St. Jude Medical as soon as possible. Notification of death should include a detailed statement of the pertinent events and be signed by the investigator in addition to the appropriate case report forms (Death form, Withdrawal form, and Product Out of Service form). A Mortality Committee will review and classify all patient deaths. It is the investigator's responsibility to notify the IRB/MEC per the IRB/MEC policy. Details of death and the following information, if available, should be provided in a letter to St. Jude Medical by the investigator summarizing the patient's course since enrollment in the study:

- Date and time of death

- Place death occurred (e.g., hospital, nursing home, patients home)
- If death was witnessed
- Identification of the rhythm at the time of death, if known (include any available documentation)
- Cause of death
- Any other circumstances surrounding the death
- Approximate time interval to death from the initiating event.
- Autopsy report (if performed)
- Whether it was device and/or procedure related
- Whether it was related to the study
- Device configuration at the time of death

Provide clinical notes and witness statements. If possible, interrogate the pulse generator. Retrieve and print all episode diagnostics, IEGMs, and programmed parameters. If applicable, the pulse generator should then be programmed OFF.

Every attempt should be made to explant the pulse generator and/or leads intact. Any explanted devices or leads (including damaged leads, lead segments and lead fragments) should be returned to St. Jude Medical for analysis promptly. In the event that the device is not explanted, the above procedure must be followed to retrieve the data. The reason the pulse generator and/or lead(s) are not being returned to St. Jude Medical must be stated clearly on the case report form.

15.0 Patient Relocation

If a patient moves from the geographic catchment area of their investigator, then St. Jude Medical (SJM) will first attempt to place the patient with another Optisure investigator. If it is not possible to place the patient with another Optisure investigator, then SJM will request that the patient's new physician forward the patient's study information to the investigator. If patient follow up information is not forwarded to the investigator the patient will be considered lost to follow up per the lost to follow up definition in section 16.0.

16.0 Withdrawals

Withdrawal is defined as termination of participation of a patient from a clinical study. All reasonable efforts should be made to retain the subject in the clinical study until completion of the clinical study. Reasons for withdrawal include, but are not limited to the following:

- Patient Death
- Patient and/or Family Request
- Patient Lost to Follow-Up - Defined as the following: Patient will be considered "lost to follow-up" after a minimum of two documented phone calls were made by personnel at the study center to the patient or emergency contact, a certified letter was sent to the last known address, and two consecutive visits pass without an investigator receiving data
- Patient Non-compliance

- Patient Participation terminated by Investigator
- Sponsor Request
- Unsuccessful Implant
- Heart transplant
- Optisure lead removed or capped without a Optisure lead replacement

A Withdrawal Case Report Form should be completed and submitted to St. Jude Medical using the EDC system. **If there is a potential withdrawal in the study, please contact a member of the study team to see if there is anything that can be done to keep the patient in the study.**

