2.0 Purpose

The purpose of this post approval study is to characterize the chronic performance of the SJM Optisure family of HV leads in patients that have an approved indication, as per ACC/AHA/HRS/ESC guidelines, for implantation of an ICD or CRT-D system for treatment of heart failure or life-threatening ventricular tachyarrhythmia, and who meet all the inclusion/exclusion criteria. The Optisure lead study will be performed in compliance with the Conditions for Approval as agreed upon with the FDA. If during the course of the study a future generation of the Optisure RV lead is approved, these devices may be included in the study upon agreement with the FDA.

The following objectives will be evaluated in the post approval study:

1. To determine the Optisure lead related complication free rate at 5 years
2. To document all Optisure lead related adverse events

Additionally, the following objectives will be evaluated in a subset of patients in the Optisure lead study who agree to participate in a sub-study:

1. To determine the incidence of externalized conductors after enrollment
2. To determine the incidence of other visual lead anomalies by each subcategory per Appendix A after enrollment
3. To determine the incidence of electrical dysfunction[§] after enrollment
4. To evaluate the 30-day adverse event rate associated with lead revision procedures (include lead extractions or abandonments with or without lead replacement)
5. To determine the prevalence of “other insulation anomalies” in returned Optisure leads:
 - Internal abrasion short under RV shock coil
 - Internal abrasion short under SVC shock coil
 - Exposed conductors defined as a breach of the outer insulation and/or breach of the internal silicone lumen tubing, but the conductor cable is contained within the lead body diameter.

[§]”Electrical dysfunction” is determined to be present after adjudication of the following cases of potential electrical failures that led to the lead being either surgically capped/extracted or electrically abandoned. Potential electrical failures include the following:

- Presence of non-physiologic noise not due to external interference
- Rise in pace/sense (p/s) conductor impedance to $> 2000 \Omega$ or increase of more than 200Ω over previous 6 months or increase of 400Ω over any period of time
- Decrease of more than 200Ω over previous 6 months or to impedance $< 200 \Omega$ from baseline impedance $> 300 \Omega$ or decrease of 400Ω over any period of time

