5.3.6 Time from other visual lead anomalies by each subcategory to electrical dysfunction

Lead Population

All Optisure leads with other visual lead anomalies (by each subcategory) but without electrical dysfunction.

Analysis:

Time to electrical dysfunction will be analyzed using the Kaplan-Meier method. The zero time will be the date at which other visual lead anomaly (by each subcategory) was detected. Those patients who experience other visual lead anomaly (by each subcategory) after enrollment, but do not experience an electrical dysfunction will be censored 3 years after enrollment in this trial.

5.3.7 Adverse Event rate through 30 days post-intervention for lead (e.g. extraction, abandonment, revision, other)

Lead Population

All Optisure leads that require an intervention/revision (e.g. extraction, abandonment, other).

Analysis

The 30-day adverse event rate will be calculated as the number of adverse events within 30 days associated with lead related interventions divided by total lead related interventions.

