9.2.2 Unsuccessful Implant– if applicable

Enrolled patients who have an unsuccessful implantation of a St. Jude Medical Optisure lead (see definition for successful Optisure lead implant in section 4.2) will be followed for a period of 30 days for adverse events and then withdrawn from the study unless the implant will be re-attempted within 30 days of the unsuccessful implant. The physician may re-attempt the implantation of a St. Jude Medical Optisure lead at his/her discretion.

In addition to the Forms identified in section 9.2.1 complete the Out of Service for any product used but not implanted (e.g. contaminated, dropped or opened in error) and record all results. After 30 days, if the patient has not had an implant re-attempted, complete a Withdrawal Case Report Form and record all results. Submit the forms to St. Jude Medical using the EDC system.

If the physician chooses to re-attempt the implantation of a St. Jude Medical Optisure lead within 30 days, complete Implant and Lead Measurements Case Report Forms, an Adverse Event Case Report Form (if applicable) and Out of Service Case Report Form (if applicable) and record all results. Submit the forms to St. Jude Medical using the EDC system.

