9.4 Follow-Up Requirements

Lead measurements and adverse events (if applicable) will be obtained every 6 months from patients who have a successfully implanted Optisure lead until they reach the 5 year follow-up.

The schedule of follow-ups is based on the date of a successful Optisure lead implant. Table 4 outlines the time window that is permitted for each of the study interval visits.

Table 4: Study Interval Time Windows

Every 6 months thereafter until 5 years
± 90 days

The following electrical measurements* will be obtained at each follow up: capture thresholds for all implanted leads, signal amplitude measurements for the RV and RA leads, pacing lead impedance for all implanted leads and high voltage lead impedance for all implanted leads.

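### Section 16.0 allows withdrawal as soon as an Optisure lead is removed or capped without an Optisure replacement, so the 30-day window needed for sub-study objective 4 and outcome 5.3.7 is not secured

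*Protocol*

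**What the plan says.** Sub-study objective 4 in section 2.0 reads "To evaluate the 30-day adverse event rate associated with lead revision procedures (include lead extractions or abandonments with or without lead replacement". Section 5.3.7 turns this into a rate. The numerator is defined by "The 30-day adverse event rate will be calculated as the number of adverse events within 30 days associated with lead related interventions", and this is "divided by total lead related interventions".

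Section 16.0 states: "Withdrawal is defined as termination of participation of a patient from a clinical study". Its list of reasons includes "Optisure lead removed or capped without a Optisure lead replacement", with no date and no minimum observation attached. A replacement of another make also falls under this item.

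Section 11.0 sets the reporting window: "Should an adverse event occur at any time between implant and withdrawal, complete an Adverse Event form". Section 9.4 sets the routine schedule: "Lead measurements and adverse events (if applicable) will be obtained every 6 months from patients who have a successfully implanted Optisure lead". Section 9.3 on system revisions asks for imaging, testing, forms and return of the product, but for no contact at 30 days.

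For an unsuccessful implant the protocol is explicit. Under section 9.2.2 such patients "will be followed for a period of 30 days for adverse events and then withdrawn from the study" unless a new attempt is made within that time, and section 4.1 agrees.

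**The concern.** The event that places a patient in the no-replacement part of objective 4 is also a listed ground for ending that patient's participation. Once withdrawal is recorded, the site has no duty to report what happens in the rest of the 30 days. The intervention itself is already documented and counts in the denominator.

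What is at stake is a safety rate in a study run under FDA conditions of approval. Extractions and cappings that end without an Optisure lead need not carry the same risk as an exchange of one Optisure lead for another, and they are the ones with incomplete observation. How incomplete depends on when each site files the withdrawal form. An analysis plan cannot repair this later, because it cannot recover events that sites were never asked to collect.

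**Working it through.** The protocol gives no figure to reproduce here, so the check is first a reading of the sections together and then an illustration of size.

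**Step 1: the sections side by side**

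| Question | Section | Answer |
|---|---|---|
| Which interventions count? | 2.0, 5.3.7 | All lead-related interventions, with or without replacement |
| For how long are events needed? | 5.3.7 | 30 days after the intervention |
| What can end participation? | 16.0 | Removal or capping without an Optisure replacement; no timing given |
| Until when are adverse event forms required? | 11.0 | Until withdrawal |
| Does the revision section add a 30-day contact? | 9.3 | No |
| Do routine visits cover it? | 9.4 | No: every 6 months, and tied to a successfully implanted Optisure lead |
| Is a 30-day hold written anywhere? | 4.1, 9.2.2 | Yes, for unsuccessful implants only |

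Section 11.0 also sends events that occur between visits to the next scheduled visit. A withdrawn patient has no next visit.

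**Step 2: direction**

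Let N be the number of interventions, r the true number of 30-day events per intervention, q the share of interventions that end in removal or capping without an Optisure replacement, and f the share of their 30-day events that falls after withdrawal. Take r as equal in both groups.

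- Events that can be reported: N×r×(1 - q) + N×r×q×(1 - f) = N×r×(1 - q×f)
- Denominator: N
- Reported/true = 1 - q×f

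The ratio cannot exceed 1, so this mechanism can only lower the rate. If the event rates differ, q is replaced by the share of all 30-day events that follow no-replacement interventions, and the direction is the same.

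**Step 3: range**

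Both q and f are assumptions; the protocol gives neither.

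| q | f = 0.25 | f = 0.5 | f = 1 |
|---|---|---|---|
| 0.10 | 0.975 | 0.95 | 0.90 |
| 0.25 | 0.938 | 0.875 | 0.75 |
| 0.30 | 0.925 | 0.85 | 0.70 |
| 0.50 | 0.875 | 0.75 | 0.50 |

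For an assumed true rate of 10%, q = 0.3 gives 8.5% (f = 0.5) to 7% (f = 1), and q = 0.5 gives 7.5% to 5%.

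**Step 4: how many interventions**

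The sub-study plans 417 patients. Suppose interventions occur at the protocol's assumed lead complication rates: 3.5% (section 5.2.1), or 5% (the complement of the 95% complication-free survival in section 5.1.1). Then 417 × 0.035 = 14.6 and 417 × 0.05 = 20.9, or about 15 to 21 interventions before attrition. Interventions for other causes could add some. The no-replacement cases are a fraction of these.

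**The case against.** The strongest reply is that section 16.0 lists reasons and sets no dates. Unsuccessful implant stands in the same list, equally bare, yet those patients are followed for 30 days first. The section also asks sites to make reasonable efforts to retain patients and to contact the study team before a withdrawal. The Re-Implant definition in section 4.2 implies that some patients remain in the study between removal of the lead and a new procedure.

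This stands in part. A reader might infer that the 30-day rate after these procedures is simply not observed. The documents do not support that: a site may withdraw the patient after day 30, and events up to withdrawal, including those on the day of the procedure, remain reportable under sections 9.3 and 11.0. But the comparison with unsuccessful implants also shows the gap. For that item other sections supply the 30-day rule; for removed or capped leads none does. The Re-Implant definition confirms that the timing is open, not that the window is covered.

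Three other replies hold:

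- Section 2.0 names electrical abandonment separately from surgical capping or extraction, and section 16.0 mentions only removal or capping. Leads abandoned only electrically are therefore not clearly affected.
- The value f = 1 requires that no event occurs before withdrawal is recorded, so the halving at q = 0.5 is an extreme bound.
- Outcome 5.3.7 is one of eleven sub-study measures. It is descriptive, with no hypothesis and no sample size of its own, and few interventions are expected.

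**Conclusion.** The conflict is real but limited. Objective 4 and section 5.3.7 need a 30-day window that sections 11.0 and 16.0, followed as written, do not secure after removal or capping without an Optisure replacement. Any resulting error in the 5.3.7 rate is downward. Its size cannot be derived from the protocol; the ratios above rest on assumed q and f and on equal event rates.

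A reader might extend this to the primary endpoint or to the all-cause death analysis in section 6.2. Neither extension carries weight. The primary hypothesis concerns complications of the Optisure lead, and it is not affected by follow-up after that lead has left service. The all-cause death curve would lose at most 30 days of observation from this gap in each of a few patients, in a study that already plans for 22% non-death attrition over 5 years.

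The point is of moderate severity and is a cheap improvement; it is not a condition for the study to be valid.

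**What to change.** 1. In section 16.0, with a cross-reference in 9.3, state that after an Optisure lead is removed or capped without an Optisure replacement, the patient is followed for adverse events and death for 30 days after the procedure and only then withdrawn. A patient who is re-implanted with an Optisure lead within that time stays in the study and is not withdrawn.
2. In section 5.3.7, keep all lead-related interventions as the denominator and report how many have incomplete 30-day follow-up. Do not restrict the denominator to interventions with full follow-up or an early event: that keeps early leavers who had an event, drops those who did not, and pushes the rate up.
3. State that risk time in the lead-related time-to-event analyses ends on the date of removal or capping. Section 5.1.1 now censors at withdrawal, so without this sentence the added 30 days would count as lead exposure.
4. Do not add electrical abandonment to the withdrawal reasons. Section 16.0 does not list it now, and adding it could remove patients who at present stay in follow-up.

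The cost is a few sentences and one adverse event contact at day 30 per affected patient, on the model sites already use for unsuccessful implants. The change concerns data collection only.
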